## NON-INTERVENTIONAL (NI) STUDY PROTOCOL

### Study information

Title	IMmunization to Prevent Acute COPD Exacerbations (IMPACE STUDY)
Protocol number	PFI-INM-2016-01 (B1851177)
Protocol version identifier	Version 2
Date of last version of protocol	31 October 2016
Active substance	Pneumococcal 13-valent conjugate vaccine (diphtheria CRM197 Protein)
Medicinal product	Prevnar13
Research question and objectives	To evaluate the impact of vaccination with PCV13 on the reduction of the risk of moderate/severe exacerbations (see definitions), after 2 years of follow up and to determine which subgroup of patients benefit most from vaccination with PCV13
Author	Redacted [REDACTED SECTION]

Redacted

[REDACTED SECTION]

[REDACTED SECTION]

This document contains confidential information belonging to Pfizer. Except as otherwise agreed to in writing, by accepting or reviewing this document, you agree to hold this information in confidence and not copy or disclose it to others (except where required by applicable law) or use it for unauthorized purposes. In the event of any actual or suspected breach of this obligation, Pfizer must be promptly notified.

Redacted

## 1. LIST OF ABBREVIATIONS

Abbreviation	Definition
COPD	Chronic Obstructive Pulmonary Disease
AECOPD	Acute Exacerbation of COPD
CAP	Community acquired pneumonia
P-CAP	Pneumococcal Community Acquired Pneumonia
PCV13	13 valent pneumococcal conjugate vaccine
PPV23	23 valent pneumococcal polysaccharide vaccine
FSFV	First subject first visit
FEV1	Forced expiratory volume in 1 second
FVC	Forced vital capacity
CRF	Case Report Form
EDP	Exposure During Pregnancy
HCP	Healthcare practitioner
IEC	Independent Ethic Committee
IRB	Institutional Review Board
LSLV	Last Subject Last Visit
NIS	Non-Interventional Study
SAE	Serious Adverse Event
AE	Adverse Event
AEM	Adverse Event Monitoring

Redacted

#### STUDY TITLE

IMmunization to Prevent Acute COPD Exacerbations (IMPACE STUDY)

PROTOCOL CODE: B1851177

#### STUDY SITES:

It has been initially estimated as optimum that patient inclusion be performed in 6 different geographical areas in Spain (Salamanca, Cantabria, Palma de Mallorca, Madrid, Barcelona and Seville), involving 1 hospital in each region.

#### IEC EVALUATING IT

- This protocol will be submitted for approval to a reference IEC (Hospital Clínico de Salamanca) and for classification to the Ministry of Health according to Spanish regulation.
- It is the responsibility of the investigator to have prospective approval of the study protocol, protocol amendments, and informed consent forms, and other relevant documents, if

Redacted

applicable, from the IRB/IEC. All correspondence with the IRB/IEC should be retained in the Investigator File. Copies of IRB/IEC approvals should be forwarded to Pfizer.

- The study will not start until every needed approval of the study protocol and other essential documents will be obtained.
- The study investigator, or a study person designated by the investigator, will obtain written informed consent from each subject or the patient's legally acceptable representative before any study-specific activity is performed.

## STUDY OBJECTIVES

- **Primary objectives**

1. Evaluate the impact of routine clinical practice vaccination with PCV13 on the reduction of the risk of moderate/severe COPD exacerbations (see definitions) in adults, after 2 years of follow up.
2. Determine which subgroup of patients (based on the severity of COPD) benefit most from vaccination with PCV13

COPD severity (GOLD)

- GRADE 1: Mild/unknown [FEV1≤ 80%, FEV1/FVC < 0,7 or no spirometry data]
- GRADE 2: Moderate [50% ≤ FEV1< 80%, FEV1/FVC < 0,7]
- GRADE 3: Severe [30% ≤ FEV1 < 50%, FEV1/FVC < 0,7]
- GRADE 4: Very severe [FEV1< 30% o FEV1< 50% plus respiratory failure, FEV1/FVC < 0,7])

- **Secondary objectives**

1. Evaluate the impact of influenza and PCV13 vaccination on the reduction of the risk of exacerbations
2. Evaluate the impact of vaccination with PCV13 on patients' quality of life
3. Evaluate the impact of vaccination with PCV13 on the decrease of FEV1
4. Estimate the potential economic savings for the healthcare system derived from vaccination of COPD patients with PCV13
5. Determine the prevalence of PCV13 vaccination in COPD patients.

## DESIGN

Prospective multicenter observational study, carried out in 6 different geographical areas in Spain (Salamanca, Cantabria, Palma de Mallorca, Madrid, Barcelona and Seville), involving 1 hospital in each region.

Redacted

## **STUDY DISEASE**

Patients with chronic obstructive pulmonary disease (COPD) have been demonstrated to have an increased risk of pneumococcal disease. Pneumonia is frequent among patients hospitalized for COPD exacerbations and is associated with increased health care utilization and higher mortality. Up to 50%–70% of exacerbations can be attributed to respiratory infections by viruses or bacteria, even more in the most severe patients. They are often associated with the colonization of airways by multiple bacteria or viruses of low virulence that in normal conditions are parts of the normal flora of the upper airway. Current recommendations for immunization of patients with COPD include vaccination against influenza and *Streptococcus pneumoniae*.

The aim of this study is to generate evidence to support vaccination of COPD patients with PCV13 and/or against influenza in terms of clinical benefits and also quality of life.

## **STUDY POPULATION AND TOTAL NO. OF SUBJECTS**

Periodic follow up of COPD patients is usually performed at ambulatory setting (may be at hospital or primary care centers). Commonly, databases containing clinical information for a patient are accessible from both settings, so data from previous years would be available to compare with data captured prospectively to the same standards.

Subjects identified with COPD will be informed about the study and invited to participate by investigators at the time of their routine control visits. All therapies will be prescribed according to the updated National COPD Guidelines (GesEPOC) indicating among other therapies active reduction of risk factors, influenza and pneumococcal vaccination (with PCV13) in all patients with mild, moderate or severe COPD. All the patients will be counselled to stop smoking and advised on life-style modifications. Any vaccination will be prescribed according to clinical practice and not related to the decision to include the subjects in the study. Subjects may be vaccinated before or after inclusion in the study.

Considering that 37% of COPD patients would have a moderate/severe exacerbation per year, and assuming that at least 35% of patients will follow their pulmonologist vaccination recommendation, to have at least 200 vaccinated COPD patients with moderate/severe exacerbations, a total sample of 1541 eligible COPD patients should be included in the analysis.

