#### **8.5. Study size**

With 35% patients vaccinated with PCV13, enrolling 1540 eligible COPD patients will provide approximate 540 patients in PCV13 cohort and 1000 patients in the control cohort.

Assuming 37% of the control patients experiencing moderate/severe exacerbation per year with 70% of the patients remaining in the study at year 1, this sample size will provide 91% power to detect a statistical significant reduction of 10% on COPD moderate/severe exacerbations from PCV13 after 1-year. Assuming additional 30% dropout from year 2, the study sample size will provide 91% power to detect a statistical significant reduction of 14% on COPD moderate/severe exacerbations from PCV13 after 2-year.

Time	PCV13		Control		Power	Retention Rate
	Sample Size	% exacerbation	Sample Size	% exacerbation		
Enrollment	540		1000			
1-year	378	27%	700	37%	91.43%	70% from Enrollment
2-Year	264	60%	490	74%	91%	70% from Year 1

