5 ANALYSIS SYSTEMS / POPULATIONS

Considering that 37% of COPD patients will have one moderate/severe exacerbation per year, and assuming that at least 35% of patients will follow their doctor's vaccination

recommendation,³ to have at least 200 vaccinated COPD patients with moderate/severe exacerbations, a total of 1541 eligible subjects should be included in the analysis.

With 35% of patients vaccinated with PCV13, enrolling 1541 eligible subjects with COPD would provide approximately 540 patients in the PCV13 cohort and 1000 patients in the unexposed cohort.

Assuming that 37% of unexposed patients will present one moderate/severe exacerbation per year,² with 70% of the patients remaining in the study after 1 year, this sample size would provide 91% power to detect a statistically significant reduction of 10% in moderate/severe COPD exacerbations with PCV13 after 1 year. Assuming an additional 30% dropout in the second year, the study sample size would provide 91% power to detect a statistically significant reduction of 14% in moderate/severe COPD exacerbations with PCV13 after 2 years.

Time	PCV13		Unexposed		Power	Retention rate
	Sample size	% exacerbation	Sample size	% exacerbation		
Enrollment	540		1000			
1 year	378	27%	700	37%	91.43%	70% from enrollment
2 years	264	60%	490	74%	91%	70% from year 1

5.1 **FULL ANALYSIS**

The statistical analysis of this study will be carried out with all those evaluable patients with COPD, recruited by the Spanish sites participating in the study and who meet the following selection criteria:

5.1.1 **Inclusion Criteria**

Patients must meet all of the following inclusion criteria to be eligible for inclusion in the study:

1. *Aged 18 years or older at the time consent is given*
2. *Patient diagnosed with COPD (any stage, subgroups for analysis will be based on COPD severity)*
3. *Evidence of a personally signed and dated informed consent document indicating that the patient has been informed of all pertinent aspects of the study.*
4. *Ability to understand and complete the required quality of life questionnaires*
5. *Patients with at least 2 years of previous clinical history available relating to (if applicable) history of moderate/severe exacerbations, influenza and pneumococcal vaccination history, comorbidities and previous treatments*
6. *Spirometry data* (maximum 6 months old, or if not available at enrollment, to be performed as per normal clinical practice at visit 1 ± one month)*

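### The 200 vaccinated cases used to justify 1541 patients assume a 37% one-year rate and no loss to follow-up; the plan's own table gives 102 at 1 year and 158 at 2 years among those retained

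*Protocol*

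**What the plan says.** The protocol Abstract, under the study population and number of subjects, starts from two inputs: "Considering that 37% of COPD patients would have a moderate/severe exacerbation per year" and "assuming that at least 35% of patients will follow their pulmonologist vaccination recommendation". It concludes: "to have at least 200 vaccinated COPD patients with moderate/severe exacerbations, a total sample of 1541 eligible COPD patients should be included in the analysis". No time horizon is written beside the 200. SAP section 5 has the same argument and the same ending: "a total of 1541 eligible subjects should be included in the analysis".

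Protocol 8.5 uses practically the same number as an enrolment figure: "enrolling 1540 eligible COPD patients will provide approximate 540 patients in PCV13 cohort and 1000 patients in the control cohort". SAP section 5 does so in the paragraph after its 200-case sentence: "enrolling 1541 eligible subjects with COPD would provide approximately 540 patients in the PCV13 cohort and 1000 patients in the unexposed cohort".

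Both documents then allow for loss. The SAP's words for the first year are "with 70% of the patients remaining in the study after 1 year", and a further 30% is lost in the second year. The table printed in both places takes the PCV13 cohort from 540 to 378 to 264. It gives that cohort 27% with an exacerbation at 1 year and 60% at 2 years, against 37% and 74% in the unvaccinated cohort.

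**The concern.** The same total has two justifications, and their inputs differ. The case-count argument gives vaccinated patients the general 37% rate and loses nobody. The power argument gives vaccinated patients 27% at 1 year and loses 30% of patients in each year. Under that loss, the number enrolled and the number followed to 1 or 2 years cannot both be 1541.

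A reader of the Abstract sees only the first argument and will expect at least 200 vaccinated patients with events. If the 200 is read as a one-year count, as the 37% per year input suggests, it is about twice what the table yields among retained patients. The number of vaccinated cases also bears on the second primary objective, benefit by GOLD grade. Over four grades, 200 cases average 50 per grade and 102 average about 25. The documents do not give the actual split.

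**Working it through.** **Inputs.** Protocol Abstract and SAP section 5: 35% vaccinated, 37% with an event per year, target 200, total 1541. Protocol 8.5 and SAP section 5: 540 vaccinated patients enrolled, 378 at 1 year and 264 at 2 years; event proportions in vaccinated patients of 27% and 60%.

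**1. Reproduce the plan's figure.**
- 200 / (0.35 × 0.37) = 1544.4, against 1541 stated.
- In reverse, 1541 × 0.35 × 0.37 = 199.6.

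The figure is reproduced to rounding, but only with 37% in vaccinated patients, one year of follow-up and no loss.

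**2. Counts from the plan's table, retained patients.**
- 1 year: 378 × 0.27 = 102.1, which is 51% of 200.
- 2 years: 264 × 0.60 = 158.4, which is 79% of 200.

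**3. Which input drives the gap.**
- 1 year, no loss, 27%: 540 × 0.27 = 145.8.
- 1 year, planned loss, 37%: 378 × 0.37 = 139.9.
- 2 years, no loss, 60%: 540 × 0.60 = 324.
- 2 years, planned loss, unvaccinated rate: 264 × 0.74 = 195.4.

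At 1 year, either the lower rate or the loss is enough by itself to miss 200. At 2 years the shortfall comes from the loss.

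**4. Count early leavers as well.** This needs assumptions that the documents do not give. Take exit at mid-year, with 540 − 378 = 162 leaving in year 1 and 378 − 264 = 114 in year 2.
- Year-1 leavers: 162 × (1 − 0.73^0.5) = 162 × 0.146 = 23.6. The 1-year count becomes 102.1 + 23.6 = 126, still below 200.
- 2 years, keeping the table's 60%: the chance of no event is 0.73 after year 1 and 0.40 after year 2, so the year-2 factor is 0.40/0.73 = 0.548. By 1.5 years the risk is 1 − 0.73 × 0.548^0.5 = 0.460. Total: 158.4 + 114 × 0.460 + 23.6 = 234.
- 2 years, with the year-1 hazard held constant: the 2-year risk is 1 − 0.73² = 0.467 and the 1.5-year risk is 1 − 0.73^1.5 = 0.376. Total: 264 × 0.467 + 114 × 0.376 + 23.6 = 123.3 + 42.9 + 23.6 = 190. This replaces the table's 60% by 46.7%.

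The 2-year count therefore runs from about 190 to 234, on either side of 200.

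**5. Does power depend on the 200?** No. A two-proportion calculation with 378 and 700 patients, 27% and 37%, and two-sided 5% (sidedness is not stated and is assumed) gives 91.9%, against 91.43% stated. The power figure already uses the retained numbers.

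**The case against.** The strongest reply has four parts.

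- **Horizon.** The 200 carries no written horizon, and the objective is set at 2 years. This stands. It is why the one-year reading has to be given as the only one that reproduces 1541, and not as something the text says.
- **Analysis set.** SAP 5.1 analyses all evaluable patients who meet the selection criteria, not only completers, and the exacerbation indices in SAP 8.2.3.1 divide by each patient's own follow-up time. Early leavers may therefore contribute, and retained-only counts may be too low. This also stands, and it is why step 4 is needed. It does not rescue the one-year count, which cannot exceed 146 at the table's 27%.
- **A second rationale.** Protocol 8.5 gives a power rationale that already allows for loss. This is correct, so the 200-case sentence is the only size rationale in the Abstract but not in the plan.
- **The 37%.** The Abstract presents it as a rate for COPD patients in general, and only 8.5 assigns it to controls. That is fair, but the same plan still gives vaccinated patients 27%.

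A reader might infer that the study cannot produce 200 vaccinated cases at all, or that its power is overstated. The documents support neither. The 2-year count with early leavers straddles 200, and the power was computed on 378/700 and 264/490. The gap between 1541 and 1545 is rounding and carries no weight.

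**Conclusion.** The point holds as an inconsistency within the plan. The sentence that justifies 1541 by at least 200 vaccinated cases uses a rate and a retention that the study-size table contradicts. On the table's inputs the expected numbers are 102 at 1 year among those retained (146 with no loss at all) and 158 at 2 years among those retained. These are direct products of the plan's figures and need no outside assumption.

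A shortfall at 1 year is shown. A shortfall at 2 years is shown only among retained patients. With early leavers included, the answer turns on exit times and on the shape of the hazard, neither of which is stated. The total of 1540/1541 and the power claim are not undermined by this point.

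**What to change.** In the protocol Abstract and in SAP section 5:

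- Call 1540/1541 the number enrolled, use one figure throughout, and drop the statement that this number is to be in the analysis.
- Delete the 200-case sentence, or replace it with the expected vaccinated patients with a moderate/severe exacerbation from the plan's own table: 102 at 1 year and 158 at 2 years, among those retained, with the horizon stated.
- Refer to protocol 8.5 for the sample size rationale.

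The counts that include early leavers should stay out of both documents, because they rest on assumptions the plan does not make.

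The cost is a sentence or two in each document and a less favourable stated count. No patients are added and no analysis changes. When 8.5 becomes the single reference, its 2-year power should be checked separately: 264 and 490 patients with 60% and 74% give about 97.5% at two-sided 5%, not the 91% stated.

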## **CALENDAR**

- Protocol submission to IEC and to the Ministry of Health is expected to be done by September 2016 in order to obtain approvals in November 2016.
- Financial agreements with the sites are expected to be obtained from December 2016 to February 2017.
- Recruitment of participant subjects is expected to start (FSFV) in January 2017. The recruitment will end in January 2019.
- Database is expected to be completed and closed by April 2019. Data analysis is expected by September 2019. Study results are expected by October 2019.

Pneumococcal 13-valent conjugate vaccine (diphtheria CRM197 Protein)

B1851177

NON-INTERVENTIONAL STUDY PROTOCOL

31 October 2016

---

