## 5. MILESTONES

Milestone	Planned date
Completion of site selection	1 July 2016
Start of data collection (FSFV)	8 January 2017
End of data collection (LSLV)	31 January 2019
Study results	1 September 2019
Final study report	31 October 2019

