## 7. RESEARCH QUESTION AND OBJECTIVES

- **Primary objectives**

1. Evaluate the impact of routine clinical practice vaccination with PCV13 on the reduction of the risk of COPD moderate/severe exacerbations (see definitions) in adults, after 2 years of follow up.
2. Determine which subgroup of patients (based on the severity of COPD) benefit most from vaccination with PCV13  
COPD severity (GOLD)
  - GRADE 1: Mild/unknown [FEV1≤ 80%, FEV1/FVC < 0,7 or no spirometry data]
  - GRADE 2: Moderate [50% ≤ FEV1< 80%, FEV1/FVC < 0,7]
  - GRADE 3: Severe [30% ≤ FEV1 < 50%, FEV1/FVC < 0,7]
  - GRADE 4: Very severe [FEV1< 30% o FEV1< 50% plus respiratory failure, FEV1/FVC < 0,7])

- **Secondary objectives**

1. Evaluate the impact of influenza and PCV13 vaccination on the reduction of the risk of exacerbations
2. Evaluate the impact of vaccination with PCV13 on patients' quality of life
3. Evaluate the impact of vaccination with PCV13 on the decrease of FEV1
4. Estimate the potential economic savings for the healthcare system derived from vaccination of COPD patients with PCV13
5. Determine the prevalence of PCV13 vaccination in COPD patients.

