## **Study procedures**

Subjects identified with COPD will be informed about the study and invited to participate by investigators at the time of their routine control visits. All therapies will be prescribed according to the updated National COPD Guidelines (GesEPOC) indicating among other therapies active reduction of risk factors, influenza and pneumococcal vaccination (with PCV13) in all patients with mild, moderate or severe COPD. All the patients will be counselled to stop smoking and advised on life-style modifications. Any vaccination will be prescribed according to clinical practice and not related to the decision to include the subjects in the study. Subjects may be vaccinated before or after inclusion in the study.

Study will include periodic scheduled visits for all patients, to complete a total follow up of 2 years (see Table 1).

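### The planned last visit (31 January 2019) falls only 24.7 months after first enrolment, so almost no patient can complete the 2-year follow-up that defines the primary objective

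*Protocol*

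**What the plan says.** The dates are in two places in the protocol.

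- Section 3 Abstract, Calendar: "Recruitment of participant subjects is expected to start (FSFV) in January 2017. The recruitment will end in January 2019". The same list says "Database is expected to be completed and closed by April 2019" and "Financial agreements with the sites are expected to be obtained from December 2016 to February 2017".
- Section 5 Milestones: first subject first visit is "8 January 2017" and last subject last visit is "31 January 2019".

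The follow-up requirement is stated repeatedly.

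- Protocol 8.2, Study procedures: "Study will include periodic scheduled visits for all patients, to complete a total follow up of 2 years".
- Protocol Table 1: Visit 5 is at month 24, with spirometry and quality of life. No visit window is given.
- Protocol 7: the first primary objective is to be evaluated "after 2 years of follow up".
- Protocol 8.7: exacerbation incidence over the 2 years after inclusion is compared with the 2 years before.
- SAP 2.1 and 5 repeat the 2-year follow-up and the 2-year power row. SAP 8.2.1 plans a flow chart to month 24, and SAP 8.2.3.2 a 24-month change in spirometry.

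**The concern.** The time from first enrolment to the planned last visit is about the length of one patient's follow-up. It leaves no room for an accrual period. A patient enrolled in mid-2017 would have about 18 months of observation by 31 January 2019, and one enrolled in January 2019 almost none.

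The following all presuppose 24 months per patient: the 2-year exacerbation outcome, the 24-month FEV1 change, the month-24 quality-of-life assessment and the 2-year row of the sample-size table. If the stated last-visit date is applied, most patients are cut off administratively.

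The SAP does not deal with this. Outside the St George's questionnaire it replaces no missing values (SAP 7). The logistic model of any exacerbation during the study (SAP 8.1) has no term for length of observation, so a patient seen for three months without an event counts the same as one seen for two years.

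**Working it through.** **Inputs**

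| Quantity | Value | Source |
|---|---|---|
| First subject first visit | 8 January 2017 | Protocol 5 |
| Last subject last visit | 31 January 2019 | Protocol 5 |
| End of recruitment | January 2019 | Protocol 3, Calendar |
| Enrolment | 1540 (540 PCV13, 1000 control); 1541 in the Abstract and SAP | Protocol 8.5; Protocol 3; SAP 5 |
| Retention | 70% to year 1, then 70% to year 2 | Protocol 8.5 |
| 2-year exacerbation risk | 60% vs 74% | Protocol 8.5 |

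**The plan's own 2-year numbers.** 540 × 0.7 × 0.7 = 264.6 and 1000 × 0.7 × 0.7 = 490, matching the stated 264 and 490. The table therefore allows for dropout only and assumes that every enrolled patient has 24 months available.

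**Time available.** From 8 January 2017 to 31 January 2019 is 753 days, or 753/30.44 = 24.7 months. A month-24 visit by 31 January 2019 requires enrolment by 31 January 2017, which is 23 days after the first visit. No accrual assumption is needed for this step.

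**Share reaching month 24, with uniform accrual to 31 January 2019 (assumed)**

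- 23/753 = 3.05%, and 0.0305 × 1541 ≈ 47 patients before dropout.
- After retention, 47 × 0.49 ≈ 23 patients: 264 × 0.0305 ≈ 8 PCV13 and 490 × 0.0305 ≈ 15 control. The plan has 264 + 490 = 754.
- Reaching month 12 requires enrolment by 31 January 2018: (753 − 365)/753 = 51.5%. The interim analysis requires 75% with one year completed, so its condition would not be met by the last visit.
- Mean available follow-up: 753/2 = 376.5 days, or 12.4 months.

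**Power for 60% vs 74%** (two-sided 0.05, sidedness assumed), from Φ[(0.14 − 1.96 × SE0)/SE1], where SE0 is the pooled and SE1 the unpooled standard error:

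- Planned 264 and 490: SE0 = 0.0353, SE1 = 0.0361, so Φ(1.96) = 97.5%. The plan states 91%, so that figure does not follow from its own inputs. This is a separate matter and nothing here depends on it.
- About 8 and 15: SE0 = 0.202, SE1 = 0.206, so Φ(−1.24) = 11%.
- With no dropout at all (about 16 and 31): 17%.

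**Sensitivity**

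| Scenario | Share able to reach month 24 |
|---|---|
| Uniform accrual to 31 January 2019 | 23/753 = 3.1% |
| Uniform accrual to 1 January 2019 | 23/723 = 3.2% |
| Accrual completed in 12 months | 23/365 = 6.3% |
| Accrual completed in 6 months | 23/182.5 = 12.6% |
| Accrual to 31 January 2019, month-24 visit allowed one month early | 51/753 = 6.8% (about 104 patients) |
| Accrual to 31 January 2019, data collected to 30 April 2019, past the stated last visit | 112/753 = 14.9% (about 229 patients; power about 34% after dropout) |

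**Recruitment read as data collection.** The last visit stays on 31 January 2019, so full follow-up would need 1540 patients in 23 days at 6 hospitals: 1540/6 ≈ 257 per hospital, invited at routine visits, while site agreements are expected to run into February 2017.

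**The case against.** The strongest reply is that this is a calendar slip and the design is sound. Twenty-four months per patient is stated consistently throughout both documents, the SAP sets no calendar cut-off, and the conflicting dates are labelled planned or expected. The drafter may have added 24 months to first enrolment and forgotten the accrual period. If the visit schedule governs in practice, nobody is truncated and only the lock moves. That may well be what was intended, but the documents do not say which governs, and the stated last visit, database closure and report dates all follow the short calendar.

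A second reply is that the indices in SAP 8.2.3.1 divide exacerbations by each patient's own time, so partial follow-up is still usable. This is correct: the study would not be without data. However, those indices run from COPD diagnosis or from vaccination over variable periods. They do not give the 2-year outcome after inclusion, the 24-month FEV1 change, or a yes/no model with comparable observation.

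A third reply is that 3.1% is one scenario. That is fair, and the table above gives the range. The site-agreement dates are supporting evidence only: sites that signed in December or January could enrol in January. They point to slow early accrual, which would lower the share.

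**Conclusion.** The concern holds and must be fixed. The protocol's dates agree with each other but cannot be reconciled with 24 months of follow-up for all patients. With a last visit on 31 January 2019, nobody enrolled after January 2017 can reach month 24 without an early-visit allowance, which the protocol does not give.

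Under uniform accrual about 3% of patients (47 of 1541) could reach month 24, and about 23 would remain after planned dropout against 754 assumed. Across the other accrual and cut-off scenarios the share stays at or below about 15%. The exact share depends on an accrual pattern that the documents do not give. The consequence for the primary objective depends on the stated last-visit date being applied as written.

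**What to change.** Amend the Calendar and Milestones so that last subject last visit equals last enrolment plus 24 months. There are two ways to do this.

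- Keep recruitment to 31 January 2019 and move the last visit to 31 January 2021. Holding the present intervals, a 24-month shift takes database closure from April 2019 to April 2021 and the final report from 31 October 2019 to 31 October 2021.
- State an earlier close of recruitment that the six sites can achieve, and set the last visit 24 months after it.

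In either case, state the accrual period explicitly and add a visit window for month 24 to Table 1.

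Only if the sponsor keeps 31 January 2019 as the last visit should the horizon change. The primary objective would then be restated as an exacerbation rate over available follow-up, and the 2-year power row and 24-month change endpoints removed from the protocol and SAP.

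The cost is one protocol amendment. Correcting the dates adds no visits or procedures for any patient, because the month-24 visit is already planned; the downside is a later lock and report. Keeping the January 2019 date avoids that delay but gives up the 2-year question.
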